1.6.6 Other Assessment

Subjects will rate the comfort of IP instillation at Days 1, 7, 14, 28, 56, 84 according to the following 4-point scale:

- 0 = No discomfort
- 1 = Mild discomfort
- 2 = Moderate discomfort
- 3 = Severe discomfort

1.6.7 Subject Withdrawal Criteria

The following are the criteria for considering withdrawal from the study:

- Withdrawal of subject consent. The subject may request for any reason at any time to be withdrawn from the study.
- The Sponsor terminates the study.

If a subject withdraws from the study, the reason for withdrawal will be recorded in the eCRF.

If a study subject fails to attend a study visit at any point during the study period, every effort should be made to keep the subject in the study and conduct all study visits as scheduled; all attempts to contact the subject must be documented.

1.7 Study Data

The study data to be analyzed include all clinical data captured by eCRF. The eCRF database will be locked for the final analyses.

2 GENERAL ANALYSIS DEFINITIONS

All analysis dataset preparations and statistical analyses will be performed using SAS[®] version 9.4 or higher. No imputation will be performed for missing data unless stated otherwise. Listings for CSR Appendix 16.2 will include, as a minimum, all the subject data points to be used for analyses. Data listings will be provided for all subjects with data available.

2.1 Study Eye

Based on the protocol, for subjects with a qualifying SANDE score who meet all other inclusion/exclusion criteria, the eye with the lower TBUT at Visit 2/Day 1 will be designated as the study eye. In the event both eyes have the same TBUT scores, the eye with the lower Schirmer's test score will be designated as the study eye. If both eyes have the same TBUT and Schirmer's test scores, the right eye will be designated as the study eye.

The study eyes for analyses were based on the study eyes designated by eCRF according to above criteria.

2.2 Treatment Groups

All the analyses will be conducted by four individual treatment groups that will be labelled as 0.1% SDP-4, 1.0% SDP-4, 3.0% SDP-4, and Vehicle. The subjects receiving SDP-4 may be pooled for data summary as appropriate, and will be labeled as "All SDP-4".

2.3 Treatment Period, Visit, and Day

The overall study consists of initial Screening, Run-In, and one Treatment Period.

A reference date refers to the date of the first randomized IP administration. All efficacy and safety assessments at all visits will be assigned a day relative to this date. The relative day will be defined as: visit date – reference date + 1 for visits on or after the reference date, and visit date – reference date for visits before the

reference date.

2.4 Definition of Baseline

In general, the baseline is defined as the last assessment before the intake of the first randomized IP unless specifically stated otherwise. Pre-dose unscheduled assessments will be taken into account for baseline determination.

2.5 Out of Window and Unscheduled Visits

All scheduled assessments after first administration of randomized IP will be used. The protocol defined windows for scheduled visits will not be used in the analyses by visit. Data will be assigned to the scheduled visit closer in time to the scheduled visit. Unscheduled visit data will only be used in an analysis if there is no other available data closer in time to a scheduled visit. Post first dose unscheduled assessments will be taken into account for worst-case determination as applicable. All unscheduled visit data will be included in data listings.

2.6 Analysis Populations

2.6.1 Screened Population

All subjects who were screened and signed the informed consent are included in the Screened Population (SCRN).

2.6.2 Intent-to-Treat (ITT) Population

The ITT population will include all randomized subjects who received IP. This population will be the primary population for efficacy analyses and will be used to summarize all efficacy variables by the treatment group as randomized.

2.6.3 Per Protocol (PP) Population

The PP population is **a subset** of the ITT population, which will include all subjects who complete the study without major protocol deviations. This population will be the secondary population for efficacy analyses and will be used to summarize a subset of efficacy variables by the treatment group as treated.

2.6.4 Safety Population

All safety endpoints will be evaluated on the Safety Population (SAF), consisting of all randomized subjects who received at least one dose of randomized IP and will be analyzed by the treatment group as treated.

All protocol deviations that occur during the study will be considered for their severity/impact and will be taken into consideration when subjects are assigned to analysis populations prior to final database lock.

A summary table of number (%) of patients in each analysis population/set will be provided.

2.7 Unit of Analysis

In general, the unit of analysis will be study eye and non-study eye for eye-level measurements, and subject for subject-level measurements.

2.8 Definition of Subgroups

No subgroup analyses are planned.

2.9 Descriptive Summaries

Summary statistics and statistical analyses will generally only be performed for subjects included in the relevant analysis population. For the calculation of summary statistics and statistical analysis, unrounded data will be used. All tabulated summaries will include all 4 individual treatment groups and the All SDP-4 group (combined from the 3 SDP-4 dosing groups) as described in Section 2.2. For endpoints that are continuous in nature: number of observations, mean, median, minimum and maximum, and standard deviation (SD) values will be presented as descriptive statistics summary for both observed values and change from baseline values at each scheduled visit if applicable. For endpoints that are categorical in nature: frequency counts and percentages will be presented as descriptive statistics summary at each scheduled visit if applicable.

The number of decimal places to display for calculated data will be determined by the original scale of the data. Means and medians will be reported with one (1) additional decimal place. Standard deviation will be reported with two (2) additional decimal places. Minimum and maximum will be reported with the same number of significant digits as the method of capture.

3 SUBJECT INFORMATION

In general, all subject information will be summarized for the ITT Population based on randomized treatment group, unless stated otherwise.

3.1 Disposition Information

Summaries will be provided for number and percentage of completed or discontinued study with the reasons of discontinuation as collected on eCRF.

3.2 Study Visits

The number and percentage of subjects completing each scheduled visit will be tabulated.

3.3 Demographics and Baseline Characteristics

Descriptive statistics or frequency tabulation **will be provide**d for age, gender, race, ethnicity, and iris color.

3.4 Medical and Ocular History

A summary table will be prepared for the medical history data, and one for ocular history data. Conditions will be categorized according to Medical Dictionary for Regulatory Activities (MedDRA). This table will indicate the number and percentage of subjects who presented with previous history overall and by system organ class and preferred term.

3.5 Pregnancy Status

The data for urine pregnancy testing will be presented in a listing, for female subjects with childbearing potential only.

3.6 Protocol Deviations

All reported major protocol deviations and determined exclusions from any analysis population(s) will be documented and included in the CSR. The number and percentage of subjects who met any inclusion or exclusion exceptions will be summarized by excepted inclusion and exclusion criteria.

4 TREATMENTS AND MEDICATIONS

In general, all treatment parameters will be summarized for the Safety Population based on actual treatment group, unless stated otherwise. All reported medications will be coded using World Health Organization-Drug Dictionary (WHO-DD).

4.1 **Prior Medications**

Summary tables will be prepared for the reported use of all non-study drugs by generic name (including prescribed and over the counter medications) that were taken prior to enrollment but that were discontinued prior to receiving the first administration of the randomized study treatment at Visit 2.

4.2 Concomitant Medications

Summary tables will be prepared for the reported use of all non-study drugs by generic name (including prescribed and over the counter medications) that were taken subsequent to receiving the first administration of the randomized study treatment at Visit 2, regardless of when use started.

4.3 Extent of Exposure

4.3.1 Extent of Exposure to Run-in Study Medication

Extent of exposure to run-in study medication will be calculated as days on vehicle, defined as one plus the difference in days between the date of last instillation as recorded at Day 1 and the visit date at which medication was first dispensed (Screening).

Overall, extent of exposure to run-in study medication will be summarized using descriptive statistics. Extent of exposure to run-in study medication will also be presented (N and %) by the following intervals: 1 to 7 days, and >7 days.

4.3.2 Extent of Exposure to Randomized Study Medication

Extent of exposure to randomized study medication is calculated as days on therapy, defined as one plus the difference in days between the date of last instillation and the date at which randomized medication was first dispensed. For subjects for whom the date of last dose is unknown, extent of exposure will be calculated based on the date of last contact.

Overall, extent of exposure to randomized study medication will be summarized using descriptive statistics. Extent of exposure to randomized study medication will also be presented (N and %) by the following intervals: < 8 days, 8 to 28 days, 29 to 56 days, 57 to 84 days, and > 84 days.

4.4 Artificial Tears

The amount of used and unused artificial tears will be documented by site personnel starting at Visit 2 through Visit 7 if the artificial tears were required by the subject. The number and percentage of subjects who used artificial tears at

least once during the study will be tabulated. Among subjects who used artificial tears at least once during the study, the overall amount of used artificial tears will be summarized using descriptive statistics.

Downloaded by [name] on 4/29/2020

5 EFFICACY

5.1 Efficacy Endpoints

- 5.1.1 Primary Efficacy Endpoint Mean change from baseline in total SANDE score at Visit 7/Day 84
- 5.1.2 Secondary Efficacy Endpoints
 - Mean and mean change from baseline at each visit for each of the following evaluations:
 - Conjunctival lissamine green staining (combined and each zone)
 - Corneal fluorescein staining (combined and each zone)
 - TBUT
 - Anesthetized Schirmer's test at Visit 7/Day 84
 - Conjunctival hyperemia
 - Individual symptom VAS scores, separately for each symptom
 - SANDE

 Mean and mean change from baseline in total SANDE score at each visit, excluding Visit 7/Day 84

 Mean and mean change from baseline in SANDE severity score at each visit

Mean and mean change from baseline in SANDE frequency score at each visit

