1 INTRODUCTION

This statistical analysis plan (SAP) describes the final statistical analysis for subject information, efficacy data, and safety data to be done for the study entitled "A Phase 2, Multicenter, Double-Masked, Randomized, Vehicle-Controlled, Parallel-Group, Dose-Response Study of SDP-4 Ophthalmic Solution in Subjects with Dry Eye Disease (DED)" (Date Amendment 1: 03APR2019). Mock shells are also produced as a separate working document to facilitate programming of Tables, Figures, and Listings (TFLs) according to finalized SAP. The SAP is to be interpreted in conjunction with the protocol, and supersedes the statistical considerations identified in the protocol. If the final clinical study report (CSR) contains changes to any planned statistical analyses, the justification for any such differences will be fully documented in the CSR.

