1.2 Study Design

This is a Phase 2, multicenter, double-masked, randomized, vehicle-controlled, dose-response, parallel-group study designed to evaluate the ocular and systemic safety and efficacy of SDP-4 ophthalmic solution in subjects with moderate to severe DED in both eyes (OU) over a 12-week (84-day) treatment period.

Subjects will be randomized to 1 of 3 concentrations (0.1%, 1.0% and 3.0%) of SDP-4 Ophthalmic Solution or vehicle in a 1:1:1:1 ratio, with 75 subjects randomized to each group in parallel. All investigational products (IP) (SDP-4 concentrations and vehicle) will be provided in single-use dose (SUD) containers seal packed into foil pouches.

The IP will be administered via topical ocular instillation, one drop per eye, twice daily (BID) for 12 weeks (84 days). Both eyes will be treated. A 2-week screening/run-in period on BID vehicle will precede the 12-week randomized treatment period.

Subjects must have a Symptom Assessment in Dry Eye (SANDE) total score of \geq 40 at Visit 1/Screening and Visit 2/Day 1 to enter the trial. The study will consist of 7 clinic visits, 2 visits during the screening period and 5 on treatment visits: Visit 1 (Day -14 ± 2/Screening Visit), followed by a 2-week run-in on BID vehicle, Visit 2 (Day 1/Confirmatory and Randomization Visit), Visit 3 (Day 7 ± 2), Visit 4 (Day 14 ± 2), Visit 5 (Day 28 ± 2), Visit 6 (Day 56 ± 4) and Visit 7 (Day 84 ± 4/End of Study Assessments).

If a subject complains of persistent dry eye symptoms, the site may provide the subject with unpreserved artificial tears (provided by the Sponsor), to be used

only if necessary. The subject must return all used and unused artificial tears at each visit so the site can conduct accountability to assess the use of artificial tears. Artificial tears may not be used within 2 hours prior to any study visit.

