5.2 Type 1 Error Control for Multiple Tests

In order to minimize the impact of multiplicity in this dose-response study, a gatekeeping procedure will be followed to conduct the following analyses in a hierarchical order:

- 1. Primary (SANDE) high concentration vs. vehicle
- 2. Primary (SANDE) middle concentration vs. vehicle
- 3. Primary (SANDE) low concentration vs. vehicle

The comparisons will be conducted at $\alpha = 0.05$. Each comparison will be made in order until p > (exceeds) 0.05. If p ≤ 0.05, the comparison is statistically significant and testing is continued.

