5.3 Handling of Missing Data

For efficacy analyses, use of a mixed model for repeated measures (MMRM) approach requires only that data are missing at random so that no other method will be employed to deal with missing data. It may be necessary to test whether this assumption applies to the data set. For sensitivity analysis the last observation carried forward (LOCF) will be used for missing data imputation.

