5.4 Methods of Efficacy Analysis

Each endpoint will be summarized for each visit where that endpoint is assessed. Where appropriate, the change from baseline value will be used to assess the difference between each concentration of SDP-4 and vehicle.

Change from baseline endpoints will be analyzed using MMRM analysis with terms for baseline measurement, treatment, visit, and treatment-by-visit interaction. An unstructured variance-covariance matrix will be employed to account for within subject correlation in the repeated measures. In case of model non-convergence a simpler variance-covariance matrix will be employed. Within treatment estimate of least square mean change from baseline and associated standard error will be provided by visit. Also, estimate of difference in least square means of change from baseline between each SDP-4 group and Vehicle (i.e. the estimand) and associated standard error and 95% confidence interval will be provided by visit.

The MMRM analysis is based on a standard linear mixed model, defined as:

$$Y = \mu + B_i + T_t + V_j + TV_{tj} + \underline{\varepsilon_{itj}}$$

Where **Y** denotes an outcome variable, μ is the overall mean, B_i is the baseline value, T_t is the fixed effect due to tth treatment group, V_j is the fixed effect due to the jth visit, TV_{tj} is the treatment by visit interaction, and $\underline{\varepsilon_{itj}}$ is the measurement error associated with the individual subject.

Following is a sample SAS code for MMRM analysis:

proc sort data=datain; by subject_id visit; ods select diffs lsmeans; proc mixed data=datain method=reml; class subject_id treat visit; model cfb_var= baseline treat visit visit*treat / solution rcorr; repeated visit / type=un subject=subject_id rcorr; lsmeans visit*treat / pdiff; run; guit;

For variables with only one post-baseline assessments (e.g. Schirmer's test), change from baseline will be analyzed utilizing analysis of covariance (ANCOVA) with terms for baseline measurement and treatment. The mathematical form of the ANCOVA model is also based on a standard linear mixed model, defined as:

$Y = \mu + B_i + T_t + \underline{\varepsilon_{it}}$

Where **Y** denotes an outcome variable, μ is the overall mean, B_i is the baseline value, T_t is the fixed effect due to tth treatment group, and $\underline{s_{it}}$ is the measurement error associated with the individual subject.

Following is a sample SAS code for ANCOVA analysis:

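### The SAP supplied with CS202 describes a different design, and protocol 9.5.3 taken alone does not tie the primary test to Day 56

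*SAP*

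**What the plan says.** **Protocol (original, 06 March 2020).** Two arms at 1:1 (1.0% SDP-4 or vehicle), 70 per group, 8 weeks, five visits (section 3.1). The primary endpoint is change in total SANDE at Visit 5/Day 56 (9.5.1), and the ITT population is primary (9.1, 9.3.1). Section 9.5.3 describes a repeated measures mixed model for change from baseline, with treatment as a fixed effect, baseline as covariate and visit as the repeated measure. Treatments are compared through least-squares means, with LOCF and observed-data sensitivity analyses. Detail is left to a SAP to be finalized before database lock.

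**Supplied SAP (Final 1.0, 24 June 2019).** Section 1 ties it to a protocol version given as "Date Amendment 1: 03APR2019" and adds: "The SAP is to be interpreted in conjunction with the protocol, and supersedes the statistical considerations identified in the protocol". Sections 1.2 and 5.1 set four arms, 12 weeks, seven visits and the primary endpoint "Mean change from baseline in total SANDE score at Visit 7/Day 84". Its visit numbering includes "Visit 5 (Day 28 ± 2), Visit 6 (Day 56 ± 4", so its Visit 5 is not CS202's Visit 5. Section 5.2 opens the testing sequence with "Primary (SANDE) high concentration vs. vehicle", and section 2.9 states: "All tabulated summaries will include all 4 individual treatment groups and the All SDP-4 group". On missing data, section 5.3 says: "For sensitivity analysis the last observation carried forward (LOCF) will be used for missing data imputation". Section 5.4 does give a full model: "Change from baseline endpoints will be analyzed using MMRM analysis with terms for baseline measurement, treatment, visit, and treatment-by-visit interaction", with an unstructured covariance.

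**The concern.** Two documents could direct the CS202 primary analysis, and neither, followed as written, estimates the stated primary endpoint.

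The SAP's primary visit and first-tested arm do not exist in CS202. The only CS202 active arm, 1.0%, is the SAP's middle concentration, so it is tested second, behind a comparison that cannot be made. A reader could still take the file as governing: the trial title it cites matches the CS202 synopsis title, including the dose-response wording, and it claims precedence over the protocol's statistics.

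Protocol 9.5.3 can be run, but with a single treatment term it targets an average over the on-treatment visits. At stake is whether the primary contrast is fixed before unmasking. Left open, the analyst could choose between a visit-averaged effect and a Day 56 effect after seeing data.

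**Working it through.** **1. Does the SAP fit CS202?**

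| Item | Supplied SAP | CS202 protocol |
|---|---|---|
| Date | 24 June 2019, for an amendment of 03 April 2019 | Original, 06 March 2020 (256 days after the SAP) |
| Arms | 0.1%, 1.0%, 3.0%, vehicle | 1.0%, vehicle |
| Planned N | 4 × 75 = 300 | 2 × 70 = 140 |
| Treatment; visits | 12 weeks; 7 | 8 weeks; 5 |
| Visit 5 | Day 28 | Day 56 |
| Primary visit | Visit 7/Day 84 | Visit 5/Day 56 |
| Testing | High, then middle, then low concentration | One comparison |
| Sample-size basis | 11.684 units, SD 24.5, Day 84 | 12.2 units, SDs 22.7 and 25.4, Day 56 |

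SAP section 8 also edits a hierarchy that it places in protocol section 9.5.3. The CS202 section 9.5.3 contains no hierarchy. The protocol's Introduction mentions one earlier Phase II dose-response study of 0.1%, 1.0% and 3.0%, the SAP's three concentrations.

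**2. Are the stated power figures sound?** For CS202, the common SD is √((22.7² + 25.4²)/2) = 24.09. The noncentrality is 12.2 / (24.09 × √(2/70)) = 3.00 on 138 df, which gives 84.5% at two-sided 0.05, as stated. The SAP's inputs (11.684, SD 24.5, 70 per group) give 80.0%, also as stated. Each document is right for its own design.

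**3. What does 9.5.3 estimate if read literally?** With complete data and no treatment-by-visit term, the treatment effect is a weighted average of the three visit-specific effects, with weights w = S⁻¹1 / (1′S⁻¹1), where S is the within-subject covariance over Days 14, 28 and 56. The documents give no Day 14 or Day 28 effects or SDs and no correlations, so every S and time pattern below is an assumption.

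- Equal SDs, equal correlation: weights 0.333, 0.333, 0.333.
- SDs 18, 21, 24, equal correlation ρ: weights 0.500, 0.309, 0.192 (ρ = 0.3); 0.582, 0.294, 0.123 (ρ = 0.5); 0.761, 0.263, −0.025 (ρ = 0.7).

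The target is 12.2 × Σ(weight × share of the Day 56 effect present at that visit):

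| Effect at Days 14/28/56, as % of Day 56 | Equal weights | SDs 18/21/24: ρ = 0.3, 0.5, 0.7 |
|---|---|---|
| 100/100/100 | 12.2 | 12.2, 12.2, 12.2 |
| 50/75/100 | 9.2 | 8.2, 7.8, 6.7 |
| 25/50/100 (proportional to time) | 7.1 | 5.7, 5.1, 3.6 |
| 125/110/100 (front-loaded) | 13.6 | 14.1, 14.3, 14.8 |

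For example, 25/50/100 at ρ = 0.5 gives 12.2 × (0.582 × 0.25 + 0.294 × 0.50 + 0.123 × 1) = 5.1.

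**4. What would the power of that test be?** Take SD 24.09 at every visit and equal correlation ρ. The visit average then has SD 24.09 × √((1 + 2ρ)/3). For ρ from 0.3 to 0.7, a constant effect of 12.2 gives 98% down to 91%. The 25/50/100 pattern (target 7.1) gives 66% down to 49%. The literal test could therefore have more or less power than 84.5%.

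**The case against.** The strongest reply is that this is a filing mismatch. The concentrations, the dates and the amendment cited all suggest that the file is the earlier study's SAP. Its precedence clause then refers to that study's protocol, and nothing supplied directs anyone to apply it to CS202. The protocol already promises a SAP before lock. It fixes Day 56 in 9.5.1 and powers Day 56 in 9.2, and a repeated measures model with visit as the repeated factor is commonly run with visit terms.

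Much of this stands, and it rules out several stronger readings that a reader might infer:

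- *CS202 has no SAP.* The documents show only that the supplied file does not describe CS202. A separate SAP may exist or be pending.
- *Section 9.5.3 expressly hands the visit terms, covariance and Day 56 contrast to the SAP.* The deferral is general. Those items are simply not mentioned.
- *The literal model dilutes the effect.* It does so if the effect builds over time. A front-loaded effect is inflated, and a constant one is unchanged and tested with more power.
- *IP comfort is lost.* SAP section 8 removes it from the safety assessments, but section 7 and Table 14.3.7 still summarize it.

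The reply does not close the gap. With the file set aside, no supplied document states the visit at which the least-squares means are compared or includes the term needed to compare them at one visit.

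**Conclusion.** The point holds. The supplied SAP cannot be run on CS202, since its primary visit and first-tested arm are absent; this follows directly from the two texts. That it belongs to the earlier Phase II study is probable but inferred.

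With the file set aside, 9.5.1 and 9.2 point to Day 56, while 9.5.3 as written estimates a weighted average over three visits. The two agree only if the treatment effect is constant. On the assumed patterns and covariances, the literal target ranges from about 3.6 to 14.8 against 12.2. The range shows sensitivity and does not predict what CS202 will find. The 84.5% is correct for the Day 56 two-sample comparison it describes and would not be the power of the visit-averaged test.

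This must be settled before lock because it determines the primary estimand, even if settling it means only producing an existing document.

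**What to change.** Confirm in writing that the June 2019 file does not govern CS202. Supply the CS202 SAP, or finalize one before database lock and unmasking as the protocol already promises. State the following there and align 9.5.3 with it:

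- **Model:** ITT population; MMRM on change in total SANDE with baseline, treatment, visit (Days 14, 28, 56) and treatment-by-visit terms, and unstructured covariance. SAP 5.4 already uses this form.
- **Primary estimate:** 1.0% SDP-4 minus vehicle least-squares-mean difference at Visit 5/Day 56.
- **Test:** one two-sided test at 0.05, with no dose hierarchy.
- **Keep:** the protocol's sample-size basis and its LOCF and observed-data sensitivity analyses. Define the latter, because the MMRM already uses observed data only.
- **Layout:** CS202 visit numbers and two treatment columns.

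The leftover dose-response wording in the protocol synopsis title and section 3.1 should be removed at the same time.

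The cost is SAP writing and a short clarification of 9.5.3, or little more than supplying the SAP if it already exists. No patients are added, and the stated power for the Day 56 comparison is unchanged.
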